2.2.2 Treatment, Optional Treatment, and Lower GI-aGVHD flare Treatment

Eligible subjects, weighing ≥ 50.0 kg, will be randomized to one of the two treatment arms (low dose or high dose in one of the three weight bands). The exact dose they receive at each visit will depend upon the weight band they fall into at baseline (in the range from 2.5 mg to 10 mg, see Table 4). Further details are provided in Section 4.2.1.1. Subjects who weigh 40.0– <50.0 kg will not be randomized but assigned to receive apaglutide 2.5 mg SC once weekly (LBW dose).

Subjects will receive their first dose of apaglutide concomitantly with RUX. In exceptional cases where concomitant administration is not possible, RUX should be administered at maximum 72 hours before apaglutide initiation.

Apaglutide will be administered via SC injection weekly for either 8 or 13 weeks. Subjects will be dosed weekly from Week 0 to Week 7 inclusive.

Apaglutide should be given at least until Week 8 unless the Investigator sees intolerable AEs that are clearly attributable to apaglutide. This will ensure that apaglutide is given enough time to fully establish its GI stabilization and regeneration effects. Should a worsening of a subject's GI-related symptoms occur shortly after starting apaglutide, adjustment of SS/RUX is the first recommended step.

If there is no complete lower GI-aGVHD response at Week 8, subjects will continue treatment from Week 8 to Week 12 inclusive. Treatment between Weeks 0 and 7 or between Weeks 8 and 12 should be continued even if a complete lower GI-aGVHD response is achieved. If the Investigator concludes that a subject is still benefitting from apaglutide treatment and a subject has no complete lower GI-aGVHD response at Week 13, apaglutide can be optionally continued for a maximum of 13 additional weeks (until Week 25, inclusive) or until a complete lower GI-aGVHD response is achieved, whichever comes first.

Lower GI-aGVHD flare treatment can start as per the protocol if a subject develops a lower GI-aGVHD flare between Weeks 9 and 25, and if treatment with apaglutide was previously stopped when lower GI-aGVHD CR was achieved at Day 56 (or when PR or CR was achieved at Day 91). The definition of a lower GI-aGVHD flare is given in Appendix 16.2.

Only one event of a lower GI-aGVHD flare can be treated with apaglutide until no later than Week 25. Apaglutide can be restarted at the same dose received at randomization.

Treatment can continue for a maximum 13 weeks (until Week 25, inclusive) or until a complete lower GI-aGVHD response is achieved, whichever comes first.

If the lower GI-aGVHD flare continues after Week 25, standard aGVHD therapies should be introduced to control the lower GI-aGVHD flare.

If the lower GI-aGVHD flare is determined to be cGVHD with overlap syndrome, standard treatment of cGVHD with immunosuppressive therapy should be initiated.

2.2.3 Follow-up Period

The follow-up period will last up approximately 2 years from the first investigational medicinal product (IMP) administration and will start at different time points during the trial:

- If a complete lower GI-aGVHD response is achieved by Week 8 inclusive, the subject will transition to follow-up at Week 8. Follow-up visits at Weeks 8, 13, 17, 21, 26, 52, and 104/EOT should be performed
- If a complete lower GI-aGVHD response is achieved from Week 9 to Week 13 inclusive, the subject will transition to follow-up at Week 13. Follow-up visits at Weeks 13, 17, 21, 26, 52, and 104/EOT should be performed
- If a complete lower GI-aGVHD response is achieved during the optional treatment or lower GI-aGVHD flare treatment, the subject will transition to follow-up. E.g., if a complete lower GI-aGVHD response is achieved at Week 20, only the visits at Weeks 21, 26, 52, and 104/EOT should be performed
- In case of early treatment discontinuation, the subject will attend an early treatment discontinuation visit approximately 4 weeks (+1 week) from the last IMP dose and subsequently transition to follow-up visits at Weeks 26, 52, and 104/EOT

2.2.4 Phone Calls

Between Week 26 and Week 104/EOT, the site will contact the subject approximately every 4 weeks via telephone. Phone calls will not be made in the same week that a trial visit is scheduled. Unscheduled calls can be performed at the discretion of the Investigator.

2.2.5 Subject Treatment after End of Trial

A long-term extension trial is not planned.

2.2.6 Early Treatment Discontinuation

A subject who discontinues treatment early is NOT considered to be withdrawn from the trial, but rather the subject will be followed up until the planned Week 104/EOT visit, provided that the subject's consent has not been withdrawn.

An early treatment discontinuation visit should be scheduled approximately 4 weeks (+1 week) from the last IMP dose. The subject will then transition to follow-up visits at Weeks 26, 52, and 104/EOT. The same visit should be completed also in case of early treatment discontinuation during the optional treatment period.

The decision for early treatment discontinuation can be made by the subject, the Investigator, or Sponsor personnel. A subject has the right to prematurely discontinue

trial medication at any time, without any justification, by withdrawal from trial medication only or by withdrawal from any further participation in the trial (i.e., early trial discontinuation [see Section 2.2.7]).

Although a subject is not obliged to give his/her reason for prematurely withdrawing from the treatment or the trial, it is recommended that the Investigator makes a reasonable effort to ascertain the reason(s), while fully respecting the subject's rights.

The Investigator must discontinue trial medication for a given subject if, on balance, he/she believes that continued administration would be contrary to the best interests of the subject.

A subject who discontinues treatment early and withdraws consent to participate in any further trial assessments is considered as withdrawn from the trial and no further assessment will be collected after informed consent withdrawal.

Apaglutide should be permanently stopped under the following conditions:

- New malignancy is identified during the trial (subjects must be treated and followed up as per local guidelines and practices for those malignancies)
- In case of an elevation of laboratory parameters as reported in Table 6
- The subject is pregnant
- In case of unacceptable toxicities associated (definitely, probably, possibly related) with apaglutide

For further considerations on IMP dose reduction and temporary discontinuation, see Section 6.6.2.

The Investigator must discontinue trial medication for a given subject if, on balance, he/she believes that continued administration would be contrary to the best interests of the subject.

A subject who discontinues treatment early and withdraws consent to participate in any further trial assessments is considered as withdrawn from the trial and no further assessment will be collected after informed consent withdrawal.

Guidance on stopping rules and follow-up medical care of subjects requiring dose adjustment are described in Section 4.2.1.2.

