MAGIC grade assessment	X	X	X	X	X	X	X	X	X	X	X	X	X
Questionnaires ¹⁵	X	X	X	X	X	X	X	X	X	X	X	X	X

ADA=anti-drug antibody; CR=complete response; CT=computed tomography; ECG=electrocardiogram; eCRF=electronic Case Report Form; EO²=end of trial; GI=gastrointestinal; MAGIC= Mount Sinai Acute Graft Versus Host Disease International Consortium; MR=magnetic resonance; PK=pharmacokinetics; NA=Not applicable

Footnotes to Table 2:

1. Follow-up visits:
 - If a complete lower GI-aGVHD response is achieved by Week 8 inclusive, follow-up visits at Weeks 8, 13, 17, 21, 26, 52, and 104 should be completed
 - If a complete lower GI-aGVHD response is achieved from Week 9 to Week 13 inclusive, follow-up visits at Weeks 13, 17, 21, 26, 52, and 104 should be completed
 - If a complete lower GI-aGVHD response is achieved during the optional treatment period or lower GI-aGVHD flare treatment, perform the next follow-up visit available after a complete lower GI-aGVHD response is achieved (for example, if a complete lower GI-aGVHD response is achieved at Week 20, perform follow-up visits at Weeks 21, 26, 52, and 104)
2. In case of early treatment discontinuation, an early treatment discontinuation visit should be performed at approximately 4 weeks (+1 week) after the last IMP dose. Follow-up starts from the early treatment discontinuation visit and the subject will then transition to Weeks 26, 52, and 104 (EOT)
3. In case of early trial discontinuation, the subject will be asked to return to the site approximately 4 weeks (+1 week) from the date of early trial discontinuation. After this visit, there will be no further visits
4. All visit procedures are recommended to be done on the same day, unless otherwise specified
5. In Germany, only colonoscopy or MR enterography will be performed (not CT colonography)
6. The Day 56 lower GI biopsy is optional and should be done only if a lower GI biopsy was done prior to apaglutide therapy and if the subject is medically suitable for the procedure
7. Vital signs (blood pressure, heart rate, temperature)
8. A phone call must be performed every 4 weeks (\pm 72 hours) between Weeks 26 and 104 to collect information regarding adverse events, concomitant medications, weight changes, and other pertinent information to assess the subject's medical condition. Phone calls will not be undertaken when the subject is attending the site for a scheduled visit

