The follow-up period will last up to 2 years from the first apraglutide dose. Follow-up will start at the following occasions:

- At Week 8 (if a complete lower GI-aGVHD response is achieved at Week 8).  
Visits at Weeks 8, 13, 17, 21, 26, 52, and 104/end of trial (EOT) should be performed.
- At Week 13 (if complete lower GI-aGVHD response is achieved at Week 13).  
Visits at Weeks 13, 17, 21, 26, 52, and 104/EOT should be performed.
- Once Complete Response (CR) is achieved during the optional treatment or lower GI-aGVHD flare treatment. The visits to be performed will depend on when the subject achieve a lower GI-aGVHD CR.
- After early treatment discontinuation, the subject will perform an early treatment discontinuation visit approximately 4 weeks (+1 week) from the last apraglutide dose and subsequently transition to follow-up visits at Weeks 26, 52, and 104/EOT.

[figure not shown]
- Early Treatment Discontinuation:

In case of early treatment discontinuation, the subject will be asked to return for an early treatment discontinuation visit approximately 4 weeks (+1 week) from the last apraglutide administration. The subject will then transition to follow-up and perform Weeks 26, 52, and 104/EOT visits.

- Early Trial Discontinuation:

In case of early trial discontinuation, the subject will be asked to return to the site approximately 4 weeks (+1 week) from the date of early trial discontinuation. All the assessments foreseen at the EOT visit will be performed. After this visit, there will be no further visits.

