#### 4.3.9 Secondary Endpoints

This SAP will follow the estimand framework outlined in the ICH-E9(R1) addendum (FDA 2019) for the definition of the analysis of key secondary efficacy endpoint: Overall response on the lower GI according to MAGIC assessment.

Missing data:

- The general approach is that subjects with missing data or invalid such that the response cannot be determined will be included in the analysis as non-responders.
- Lost on follow-up: subject included but response data are missing and will be imputed as non-responder until the clinical cut-off date.
- Trial discontinuation: subject included but response data are missing and will be imputed as non-responder until the clinical cut-off date.

Censored data:

- At the time of the analysis, subject visits not yet completed and with expected date beyond the clinical cut-off date will be indicated as censored (e.g. a subject visit expected 7 days after the clinical cut-off date will be censored; for subjects deceased prior the clinical cut-off date, visits that would have occurred after the clinical cut-off date will be censored).
- If the subject scheduled visit is not expected to be completed, the visit is censored (e.g. scheduled subject visit week 12 prior the clinical cut-off but excluded for the subject who did not enter treatment extension period due to complete responder status at week 8; scheduled visit at week 11 for a subject who did not enter treatment extension period due to death at week 5).
- For all enrolled subjects, all visits covering the initial treatment phase (week 1 to 8 included) and all follow-up visits are expected to be completed.
- A censored subject visit does not contribute to the denominator of the visit.
- Across all scheduled visits, the denominator plus the number of censored subjects is constant and equal to the number of subjects in the analysis set (and treatment group when applicable).

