#### 4.3.9.2 Overall/Lower GI Response Based on MAGIC Score by Time Point

The Lower GI MAGIC score response and the total MAGIC score response will be calculated per the definition described in Appendix A based on the Lower GI MAGIC score and the total MAGIC score, respectively, at a given time point, compared to the corresponding score at Baseline. It follows that every observed Lower GI MAGIC Stage response at a time point will be classified as *Progression, Stable Disease, Partial Response, and Complete Response*. Similarly, every observed Total MAGIC score response will be classified into the same categories augmented by the Mixed Response category. Subjects with missing MAGIC assessments after the first dose of apraglutide will be included as non-responders for response rate calculation. Censored assessments will not be included in the response rate calculation. Note: if a subject initiated an additional, new systemic therapy for an earlier progression, mixed response, or non-response of aGVHD, both the lower GI-aGVHD response and the overall response at subsequent time points will be assigned as non-responders until the clinical cut-off date. Additional new systemic therapies are only those that started after the first dose of apraglutide and are captured in the CM and PR eCRF forms.

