#### **Overall Response Rate at Day 56 on the Lower GI MAGIC Score**

The key secondary objective listed in protocol is to evaluate the overall response rate (partial response [PR] and complete response [CR]) at Day 56 on the Lower GI MAGIC score in subjects with SR lower GI-aGVHD Grade II to IV MAGIC that are treated with apraglutide, SS, and RUX.

To assess the key secondary objective, the key secondary efficacy estimand is defined by the following key attributes, according to the framework provided in ICH E9(R1) (FDA 2021):

- **Treatment:** weekly subcutaneous administration of low, or high, or low body weight dose of apraglutide on top of ruxolitinib within 72 hours prior the first administration of apraglutide excluding the use of additional systemic therapy from first administration of apraglutide.
- **Population:** Subjects with SR lower GI-aGVHD.
- **Population-level summary:** the proportion of subjects achieving overall response (CR+PR) on the Lower GI MAGIC score.
- **Variable:** Overall response on the Lower GI MAGIC Score.
- **Analysis Model:** use of FAS subjects for calculation of the proportion of overall response (CR and PR) on the Lower GI MAGIC score at Day 56 with a two-sided 95% confidence interval using Clopper-Pearson exact method.
- **Intercurrent events and strategy:**

- Terminal events:
  - ICE1: as death precludes further observations, based on composite strategy, assumes non-response from death event until the Primary Analysis clinical cut-off date included.
- Treatment change:
  - ICE2: in the event of treatment discontinuation, following treatment policy strategy; if a subject withdraws from treatment, observed values will be used regardless of the ICE.
  - ICE3: in the event of pausing or dose reduction of apaglutide, following treatment policy strategy, observed values will be used regardless of the ICE.
- Additional / alternative treatment:
  - ICE4: when additional systemic therapies are used for any earlier progression, mixed response or stable aGVHD, following hypothetical strategy, observed data will be discarded, and from the point of ICE, subjects will be considered as non-responder, as if treatment failure, until the Primary Analysis clinical cut-off date included.
  - ICE5: when a subject receives Donor Lymphocyte Infusions or Stem cell boost as concomitant medication or procedures, as per “treatment policy” strategy, all observed values will be used regardless of the ICE.

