**Sensitivity Analysis for Overall Response Rate at Day 56 on the Lower GI MAGIC Score and on the Total MAGIC Score**

To evaluate the robustness of the analysis of the Day 56 secondary endpoint sensitivity analyses evaluating alternative response definitions taking account for the potential influence of intercurrent will be made. Starting from the estimand describing the analysis "Overall Response Rate at Day 56 on the Lower GI MAGIC Score", the sensitivity analysis will consider simultaneously alternative ICE strategies:

- ICE2 alternative: in the event of treatment discontinuation, following composites strategy, subjects will be considered as non-responder from the point of the ICE as if treatment failure, until the analysis clinical cut-off date included, censored beyond.
- ICE3 alternative: in the event of pausing or dose reduction of apaglutide, following composites strategy, subjects will be considered as non-responder from the point of the ICE as if treatment failure, until the analysis clinical cut-off date included, censored beyond.
- ICE6 alternative: Budesonide use or other non-absorbable steroids given orally, following composites strategy, subjects will be considered as non-responder from the point of the ICE as if treatment failure, until the analysis clinical cut-off date included, censored beyond.
- ICE10 alternative: Rux interruption, following composites strategy, subjects will be considered as non-responder, as if treatment failure from the point of the ICE until the analysis clinical cut-off date included, censored beyond.
- ICE5 alternative: Donor Lymphocyte Infusions or Stem cell boost as concomitant medication, following composites strategy, subjects will be considered as non-responder, as if treatment failure from the point of the ICE, until the analysis clinical cut-off date included, censored beyond.

*4.3.9.3 Durable overall response on the Lower GI MAGIC Score from Day 28 to Day 56*

Durable overall response rate on the Lower GI MAGIC Score from Day 28 to Day 56 is defined as the proportion of subjects who had a response (either CR responder or PR responder) on the lower GI at Day 28 and remain a CR responder or PR responder on the lower GI at Day 56.

The ICE events and strategies defined in section 4.3.9.2 will be applied consistently for the estimation of CR and PR at Day 28 and Day 56 on which relies the durable overall response on the Lower GI MAGIC score.

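### Subjects taken off apraglutide before Week 8 have no scheduled Day 56 MAGIC assessment, so the treatment-policy handling of discontinuation becomes non-response imputation for most of them

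*Protocol*

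**What the plan says.** **Schedule after an early stop.** Protocol 2.2.6 keeps the subject in the trial and schedules one discontinuation visit about 4 weeks (+1 week) after the last dose. Then: "The subject will then transition to follow-up visits at Weeks 26, 52, and 104/EOT". Protocol 2.2.3 and Table 2 footnote 2 give the same route, and SAP 2.1 repeats it: "The subject will then transition to follow-up and perform Weeks 26, 52, and 104/EOT visits". None of them lists Week 8 or Week 13 for these subjects.

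**Denominator.** SAP 4.3.9 lets a visit that is not expected be censored out of the denominator, but closes that route for the main treatment period. For all enrolled subjects, "all visits covering the initial treatment phase (week 1 to 8 included) and all follow-up visits are expected to be completed".

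**Missing values.** SAP 4.3.9.2: "Subjects with missing MAGIC assessments after the first dose of apraglutide will be included as non-responders for response rate calculation".

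**Discontinuation strategy.** ICE2 in the Day 56 estimand is treatment policy: "if a subject withdraws from treatment, observed values will be used regardless of the ICE".

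**Sensitivity analysis.** "ICE2 alternative: in the event of treatment discontinuation, following composites strategy, subjects will be considered as non-responder from the point of the ICE".

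**Visit mapping.** SAP 4.1.1 assigns scheduled visits by their eCRF label and does not window unscheduled visits. The discontinuation visit has its own column in Table B2.

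**The concern.** ICE2 needs a Day 56 measurement taken after treatment has stopped. The visit schedule does not ask for one, and the missing-data rule then supplies a failure. The report would describe the key secondary rate as treatment policy for discontinuation when, for these subjects, the value was imputed.

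The planned checks would not reveal this. The ICE2 alternative assigns the same non-response. Protocol 7.8.1 also required an analysis restricted to subjects with non-missing data; the SAP does not contain it, and its removal is not among the 12 changes listed in SAP Section 6.

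The gap also reaches duration of lower GI response. SAP Table 4-3 counts a missing assessment as an event, dated at the last evaluable assessment before the missed visit. A responder who stops drug can therefore be recorded as having lost response while still in response. Response rates at Days 91, 119 and 147 have the same exposure, because all follow-up visits are also treated as expected.

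**Working it through.** **Who is affected.** The subject must meet all of these conditions:
- discontinuation is declared before the Week 8 visit;
- the subject is still in the trial and alive (death is non-response under ICE1);
- no additional systemic therapy has been started (non-response under ICE4).

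**Can the discontinuation visit stand in for Day 56?** For a last dose at Week w on its nominal day, the visit falls on Days 7w + 28 to 7w + 35. The Day 56 window is Days 55 to 57.

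| Last dose | Visit days | Possible days inside 55–57 |
|---|---|---|
| Week 0 | 28–35 | 0 of 8 |
| Week 1 | 35–42 | 0 of 8 |
| Week 2 | 42–49 | 0 of 8 |
| Week 3 | 49–56 | 2 of 8 |
| Week 4 | 56–63 | 2 of 8 |
| Week 5 | 63–70 | 0 of 8 |
| Week 6 | 70–77 | 0 of 8 |

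Now allow the ±1-day dosing window:
- Week 3 dose on Day 20, 21 or 22: visit on Days 48–55, 49–56 or 50–57, giving 1, 2 or 3 of 8.
- Week 4 dose on Day 27, 28 or 29: visit on Days 55–62, 56–63 or 57–64, giving 3, 2 or 1 of 8.
- Week 2 reaches Day 50 at the latest and Week 5 starts at Day 62 at the earliest, so neither overlaps.

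Even when the visit falls inside the window, the SAP states no rule that turns it into a Day 56 value. The analysis-dataset specifications might; they are not among the documents.

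**Size per subject.** Each true responder scored as a failure costs 1/15 = 6.7 points in one dose arm and 1/30 = 3.3 points in the randomized total.

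**Illustration.** The starting counts are assumptions; intervals are Clopper-Pearson 95%, as in the SAP.

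| Handling of one early-stopping true responder | Result |
|---|---|
| 15 subjects, true value used | 9/15 = 60.0% (32.3–83.7) |
| 15 subjects, SAP rule | 8/15 = 53.3% (26.6–78.7) |
| 15 subjects, non-missing data only | 8/14 = 57.1% (28.9–82.3) |
| 30 subjects, true value used | 18/30 = 60.0% (40.6–77.3) |
| 30 subjects, SAP rule | 17/30 = 56.7% (37.4–74.5) |

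**Expected shift.** With k affected subjects whose true Day 56 response rate is q, the shortfall is kq/N. The documents give neither k nor q. Take k = 1, 2, 3 and let q run from 0.36 to 0.57 (the historical Day 56 and Day 28 GI rates in Protocol 7.4, borrowed only as a range):
- N = 15: 2.4–3.8, 4.8–7.6 and 7.2–11.4 points.
- N = 30: 1.2–1.9, 2.4–3.8 and 3.6–5.7 points.

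**The plan's own figure.** The plan gives no figure for this point. Its 88.2% for 5 of 7 responders (Protocol 7.4) concerns the same endpoint and is not in dispute. Taking Beta(6,3) against Beta(36,62) with a 10-point margin gives 88.6%. One recoded responder (4 of 7) would give 69.9%. That shows scale only, since SAP Section 6 item 7 drops the historical comparison from the Primary Analysis.

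**The case against.** **Last dose is not the trigger.** A reader might infer that every subject whose last dose falls at Weeks 0 to 6 lacks a Day 56 value. The documents do not support that. Table 6 in Protocol 4.2.1.2 mostly holds dosing before any permanent stop, and Protocol 5.9.2 foresees visits at which no dose is given. A subject last dosed at Week 5 and still on hold at Week 8 attends that visit, has a MAGIC assessment, and falls under ICE3 with observed values. The gap begins when discontinuation is declared. This stands, and the table above shows visit timing only, not how many subjects are affected.

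**Complete responders.** Protocol 2.2.3 and Table 2 footnote 1 give a Week 8 visit to anyone in complete lower GI response by then. A discontinuer already in complete response fits both that rule and the discontinuation rule, and precedence is not stated. For them the missing visit is one reading, not settled text. Partial responders have no such alternative.

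**The rules can be read together.** ICE2 sets the strategy, and non-response for missing data is a separate, openly stated rule that the protocol calls consistent with intent to treat. So it is too strong to say that ICE2 cannot be carried out: any Week 8 value that exists will be used. What remains is that the schedule itself creates the missing value, and the estimand text does not say that imputation is then the normal outcome.

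**Little depends on it.** The direction is downward, no historical comparison is planned for the Primary Analysis, and SAP Section 6 item 12 rules out a formal dose comparison. One subject moves the estimate 6.7 points within an interval about 51 points wide. This stands, and it limits the severity.

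**Conclusion.** The point holds for a defined group: discontinuation declared before Week 8, alive, still in the trial and without additional systemic therapy. For them the Day 56 rate is failure imputation under a treatment-policy label, and the ICE2 sensitivity analysis cannot show a difference.

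The bias can only lower the rate, by 6.7 points per affected true responder in 15 or 3.3 in 30. A reader might infer that it creates false efficacy; it does not. It could separate the two arms' descriptive rates if stops differ by dose, but no planned inference rests on that contrast.

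The conclusion assumes that sites follow the written schedule and that no unseen programming rule maps the discontinuation visit to Day 56. The number affected is unknown and may be small. Severity is minor to should-fix: the result is mislabelled rather than overturned, and the repair is cheap.

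**What to change.** 1. **Protocol 2.2.3, 2.2.6 and Table 2 footnote 2.** Add that subjects who stop apraglutide early but remain in the trial also complete the Week 8 and Week 13 MAGIC assessments when these fall after the stop. The cost is one or two extra assessments per discontinuer. This cannot recover Day 56 data already past the 01 Dec 2023 cut-off.
2. **SAP ICE2.** State what is done: treatment policy where a Day 56 assessment exists, otherwise non-response. One line.
3. **Non-missing-data analysis.** Restore the analysis in Protocol 7.8.1, or list its removal in SAP Section 6. It drops the affected subjects instead of recovering their values, and their missingness is likely to be informative.
4. **Reporting.** Give, per arm, the number of Day 56 non-responders imputed after a treatment stop, and the number of Table 4-3 events caused by a missing visit after a treatment stop. Two table rows from data already collected.
5. **Optional.** As a labelled sensitivity analysis only, use the discontinuation or unscheduled assessment nearest Day 56 within ±7 days (Days 49 to 63). At nominal dosing days this covers all 8 possible visit days for last doses at Weeks 3 and 4, 1 of 8 for Weeks 2 and 5, and none for Weeks 0, 1 and 6. It must not replace the main analysis, because SAP Section 1 says that decisions were fixed before the database snapshot.

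Items 2 to 5 can still be applied in the report or its addendum.
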